## 3.3 Secondary Endpoints

The following secondary endpoints are pre-specified for analysis.

#### 3.3.1 Hyperglycemic clamp-derived ß-cell measures

- a. First phase insulin response (incremental insulin area from 0-10 minutes after initial glucose bolus)
- b. First phase C-peptide response (incremental C-peptide area from 0-10 minutes after initial glucose bolus)
- c. Disposition index derived from a and b, using hyperglycemic clamp-derived measure of insulin sensitivity (glucose disposal rate/insulin: GDR/I)
- d. Second phase insulin response, with adjustment for insulin sensitivity
- e. AIRmax response to arginine calculated using insulin concentrations and adjusted for insulin sensitivity

#### **3.3.2 OGTT-derived** ß-cell measures

- a. Early insulin response to oral glucose (insulinogenic index:  $\Delta$  insulin from 0-30 minutes/ $\Delta$  glucose from 0-30 minutes [ $\Delta$ I/ $\Delta$ G])
- b. Early C-peptide response to oral glucose (analogous to (a))
- c. Oral disposition index (DIo; insulinogenic index adjusted for insulin sensitivity)
- d. Modeled parameters of ß-cell function (ß-cell glucose sensitivity, rate sensitivity and potentiation factor; static, dynamic, and total ß-cell glucose sensitivity)
- e. Ratios of incremental insulin/glucose (iAUCins/iAUCg) and C-peptide/glucose (iAUCcp/iAUCg) responses from 0-120 minutes
- f. Incremental glucose (iAUCg) response as a measure of glucose tolerance
- g. 2-hour glucose

- h. GLP-1 total and incremental response to oral glucose load (samples will be collected, and measured for this analysis if funding allows)
- **3.3.3** Fasting measures of glycemia and β-cell function
  - a. Glucose
  - b. Proinsulin/insulin ratio
  - c. HOMA %B (using the Oxford calculator)
  - d. HbA1c

## 3.3.4 $\alpha$ -cell Function

- a. Glucagon suppression in response to sustained hyperglycemia during the clamp (the decrement in glucagon concentration from baseline to nadir value at 100-120 minutes)
- b. Acute glucagon response arginine (the incremental increase in glucagon concentration from pre-arginine baseline for the 10 minutes after the arginine injection)
- c. OGTT-derived measures: integrated glucagon response from 0-120 minutes
- d. Fasting sample-derived measures: glucagon

#### 3.3.5 Insulin Sensitivity

- a. glucose disposal rate at steady state (100-120 minutes) divided by ambient insulin concentrations during hyperglycemic clamp
- b. Matsuda index and model-derived insulin sensitivity from OGTTs
- c. 1/fasting insulin, HOMA-S (using the Oxford calculator), and QUICKI from fasting samples

#### 3.3.6 Blood and Urine Biomarkers

- a. Adipokines/inflammatory markers including C-reactive protein (CRP): adiponectin; others contingent on funding (see above in Section 2.4.3)
- b. Non-esterified fatty acids
- c. Urine albumin/creatinine ratio
- d. DNA for future genetic analysis

## 3.3.7 Physical and Body Composition Measures

- a. Physical measures: blood pressure, body weight, body mass index, waist circumference;
- b. Total fat and lean mass; regional fat and lean mass by dual-energy X-ray absorptiometry (DEXA)
- c. Visceral, subcutaneous, hepatic and pancreatic fat by abdominal magnetic resonance imaging (MRI)

# 3.4 Treatments

#### 3.4.1 Metformin Arm

Metformin will be given at a dose of 2000 mg/d, titrated over four weeks. Study medication will be withheld the morning of each CTU visit and a new supply will be dispensed at the end of each visit. Medication compliance will be monitored by pill counts. Participants will be monitored for gastrointestinal side effects that are associated with metformin. Individuals who develop side effects will be given the option of reducing the dose. Individuals who continue to have intolerable side effects will be given the options to change to an extended release preparation at maximum tolerated dose or to discontinue metformin. Handling drop-outs and missing data is discussed under Data Analysis (section 9.6)

## 3.4.2 Gastric Band Arm

The LapBand will be placed and participants will be followed according to standard clinical practice under the supervision of [name]. Costs for these procedures will be paid by Allergan in the form of an unrestricted research grant. Pre-operative evaluation will include a psychological evaluation, a cardiac evaluation with EKG and stress testing, evaluation by an anesthesiologist, a chest X-ray and clinical lab testing (CBC, chemistries, UA, PT/PTT, hepatitis panel and, for women, pregnancy test). Participants also meet with the bariatric nutritionist for education on dietary restrictions that will apply once the band is in place.

Surgeries for placement of LapBands will be performed by [name] at the Keck Hospital of USC. The procedure is done laparoscopically on outpatients. Patients see [name] 2 weeks after surgery for wound check and suture removal. Band adjustments are performed by [name], members of his bariatric surgical team, and/or [name]. Adjustments will commence ~4 weeks after surgery and will recur every 1-3 months at the time of regular research visits. Adjustments will be made based on specific criteria consisting of symptoms of satiety and hunger, dietary history, and weight loss. Patients will revert to liquid diet for 24-48 hours after band adjustments and advance diet over the next 3-5 days. The bariatric team has an on-call system to evaluate and treat patients who have symptoms related to their bands. Post-operative laboratory assessments include CBC; chemistries; vitamin B1, B6 and B12 levels; ferritin; and 25(OH) vitamin D (see Table 2 for testing schedule).

Although both groups will be on active treatment, it is possible that glycemic control could deteriorate to a point of needing additional therapies. We will be monitoring HbA1C at six month intervals. If a value is >8.0%, we will repeat it in one month and, if it remains >8.0% we

will consider the subject to have reached a safety endpoint for the trial. We will perform end-of study visits (scheduled for 24 months in Table 3) and refer the subject for care of his/her diabetes.

## 3.4.3 FDA Compliance

Participants will have BMI 30-40 kg/m^2 and either type 2 diabetes or impaired glucose levels. Metformin is approved by the FDA for use in people with type 2 diabetes regardless of BMI. The LapBand is approved by the FDA for use in individuals with BMI>30 kg/m2 and type 2 diabetes. An Investigational Device Exemption has been obtained from the FDA for inclusion of individuals with pre-diabetes.

## 3.5 Inclusion and Exclusion Criteria

#### 3.5.1 Inclusion Criteria

- 1. Completion of at least two months in a diet, exercise and behavioral modification program within past two years
- Fasting plasma glucose >90 mg/dl *plus* 2-hour glucose ≥140 mg/dl on 75 gm OGTT *plus* HbA1C ≤7.0%. There is no lower limit for the A1C and no upper limit for the OGTT 2-hour glucose based on prior studies that allow us to identify people with falling β-cell function.
- 3. Age 22-65 years
- 4. Body mass index (BMI) 30-40 kg/m^2
- 5. For participants with diabetes, known duration <1 year
- 6. No history of use of antidiabetic medications except during pregnancy

## 3.5.2 Exclusion criteria

- 1. Contraindications to LapBand(see Appendix 1)
- Contraindication to MRI (claustrophobia; permanent metal objects such as pacemakers, prostheses, aneurysm clips)
- 3. Underlying disease(s) likely to (a) limit life span to less than study duration and/or (b) increase risk of intervention outside of the study and/or (c) limit ability to participate in outcomes assessment and/or (d) limit participation
- 4. An underlying disease known to have important effects on glucose metabolism
- 5. Active infections

- 6. Renal disease (serum creatinine ≥1.4 mg/dl for men; ≥1.3 mg/dl for women) or serum potassium abnormality (<3.4 or >5.5 mmol/l)
- 7. Anemia (hemoglobin <11g/dl in women, <12 g/dl in men) or known coagulopathy
- 8. Cardiovascular disease, including uncontrolled hypertension and symptomatic congestive heart failure. Participants must be able to safely tolerate administration of fluid/volume challenges during clamp studies.
- 9. Serum AST or ALT >3 times upper limit of normal in local clinical lab
- 10. Excessive alcohol intake
- 11. Suboptimally treated thyroid disease
- 12. Conditions or behaviors likely to affect the conduct of the BetaFat Study
  - a. Unable or unwilling to give informed consent
  - b. Unable to adequately communicate with clinic staff
  - c. Another household member is a participant or staff member in BetaFat
  - d. Current or anticipated participation in another intervention research project that would interfere with any of the interventions/outcomes in BetaFat
  - e. Likely to move away from participating clinic in next 2 years
  - f. Current (or anticipated) pregnancy and lactation.
  - g. Major psychiatric disorder that, in the opinion of clinic staff, would impede the conduct of the BetaFat study
  - h. Weight loss >7% in past two months for any reason except postpartum weight loss.

13. Additional conditions may serve as criteria for exclusion at the discretion of the local site.

Further details pertaining to exclusion criteria are specified in the Manual of Procedures.

## 4. RECRUITMENT AND RANDOMIZATION

#### 4.1 Sources of Participants

There are two primary recruitment sources where we can access existing information on age, BMI and A1C or glucose levels to greatly enhance efficiency of screening. The first source is the clinical care database (EHR) of Kaiser Permanente Southern California (KPSC – [name]). The second source is the Ambulatory Care Network (ACN) of Los Angeles County (Drs. [name] and [name]). These two sources provide access to thousands of individuals likely to meet recruitment criteria.

## 4.2 Recruitment

The primary recruitment technique is prescreening of electronic and clinical medical records to identify patients who appear to meet the age, BMI, A1C and medication criteria for the study to limit screen failure rates. In particular, for recruitment from the Ambulatory Care Network of Los Angeles County DHS, a search will be made of the LAC+USC Healthcare Network Affinity database by authorized query writers to identify patients who meet criteria for the BetaFat study as well as necessary contact information. On approval of this study by the USC HS IRB this list will be released to the BetaFat study team for storage on the secure, password protected study server. Although study data will be recorded on REDCap, the list of recruits from Affinity will not be uploaded to REDCap. Back-up recruitment techniques may include notices placed on bulletin boards at the medical centers, newspaper and radio advertisements and public service announcements, and referral from colleagues. Selection is based solely on the participant's ability to meet the criteria stated in the protocol and his/her willingness to participate in the study.

## 4.3 Informed Consent

Consent is obtained in a quiet setting prior to the initiation of any study procedures. The subject is provided adequate time to read and understand the written consent and ask questions as necessary. If they choose, they may take additional time to discuss the study with family and/or physicians outside the clinic setting. Subjects are not consented until they demonstrate adequate understanding of all aspects of the study and consent process. A copy of the consent is given to the subject. A model consent form appears in Appendix 2.

In the event a significant protocol change occurs, the informed consent will be adjusted appropriately and sites will submit the revised documents to their Institutional Review Board (IRB) for approval. Local IRBs will determine whether it is necessary to re-consent participants.

The clinical site for BetaFat will submit to the BetaFat Data Center stamped IRB approval letters and current copies of all consent forms prior to study initiation, and annually thereafter. These records will be maintained by the BetaFat Data Center as a local archive.

## 4.4 Screening

Screening will take place on the Clinical Trials Unit (CTU) at USC. Individuals will have a history and physical exam directed at study inclusion/exclusion criteria, will provide blood for clinical laboratory screening, and will have plasma glucose measured before and two hours after 75g oral glucose challenge. Qualified individuals will be asked to return for baseline testing and randomization.

## 4.5 Randomization

Individuals who complete baseline testing (described below, section 6.2) will be randomized 1:1 to banding or metformin using permuted block randomization stratified by gender, BMI (30-35 vs. 35-40 kg/m^2) and diabetes (no vs. yes when IDE approved) to minimize skewing. Individuals assigned to metformin will be given study medications and instructions at the end of the second baseline visit, to begin treatment the following day. Individuals assigned to gastric banding will be scheduled for pre-operative screening with the goal of having them undergo operation within two weeks.

## 4.6 Masking

No masking will be employed. The study team and each individual participant will be aware of his/her treatment allocation.

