#### 6.2.5 MRI Scans

Approximately 80 5mm axial slices are obtained from the top of the liver to the pelvis using a series of 10-15 second breath holds on USC's research dedicated GE Healthcare 3 Tesla magnet. The procedure takes approximately 30 minutes. Iterative decomposition of water and fat with echo asymmetry and least-squares estimation (IDEAL) is used to delineate subcutaneous and visceral fat depots and quantify organ fat. SliceOmatic (Tomovision, Inc.) is used for post-image processing to compute subcutaneous and visceral adipose tissue volume and fractional fat content of liver and pancreas.

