## 7.2.2 Safety Review Plan and Monitoring

- A. Justification of Sample Size: See Section 9.3.
- B. *Stopping Rules*: The DSMB may suggest terminating a study arm at any time for safety or efficacy reasons. Details of interim analysis plans and stopping rules can be found in Sections 9.4 and 9.5.

- C. *Safety Monitoring Committee*: The RISE Consortium will appoint an internal Safety Monitoring Committee which review AEs or other safety-related problems sent to them from the field. The RISE SMC will review AEs in a blinded manner. An external Safety Review Officer will evaluate any serious adverse events (SAE) where the SMC is not in agreement about whether the event is related to study drug as well as certain specified SAEs of concern (e.g., pancreatitis). The Safety Review Officer will not be blinded to study intervention.
- D. *Safety Review Plan*: The DSMB will meet twice yearly to review study progress and safety as described in Section 7.1.

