## 7.2.3 Confidentiality

- A. *Protection of Participant Privacy*: Participants' names are linked to study IDs only on a single recruitment database and only certified project personnel are authorized to have access to this database. Only study IDs will be used in all other study databases (e.g., for tracking and merging and sharing with other sites and the NIH). NIH has obtained a certificate of confidentiality for the entire RISE Consortium, including the BetaFat Study
- B. *Database Protection*: All hard-copy files are stored in locked cabinets within locked offices at the clinical centers. Primary electronic data are entered into and maintained on a secure USC server with two-level password protection against non-project personnel. The server is backed up daily and automatically. Data for analyses common to other studies in the RISE Consortium will be transmitted to a secure, password-protected website maintained by the RISE Coordinating Center (CoC) at George Washington University. The CoC holds no personal identifiers and stores the data on its enterprise server accessible only by approved staff.

At the end of the study, all hard copy records will be kept in a secure locale for a period dictated by local IRB and Institutional policies, as well as FDA, regulations, whichever is longest.

C. *Confidentiality during AE Reporting*: AEs and SAEs are recorded on data collection forms and reported to the Coordinating Center without personal identifiers. Identifiers on accompanying documents (such as medical records) are removed before submission to the Coordinating Center and any subsequent transfer to the Safety Monitoring Committee and/or Safety Review Officer.

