# 8.4 Tracking Adverse Events

- Serious Adverse Events: SAEs will be monitored by the RISE Safety Monitoring Committee, which will remain blinded to treatment arm. The external DSMB will monitor SAEs by treatment arm. It is important to note that all serious and unexpected AEs must be reported to the CoC, regardless of the drug-related assessment. For example, a patient struck by lightning requires a report, even though this is not likely to be a drug related event.
- Non-serious adverse events: Non-serious AEs are tabulated by the CoC in periodic reports in the same format as is done for the DSMB. Summaries of the AEs are provided to the Safety Monitoring Committee, which reviews this summary during one of its regularly scheduled meetings.
- Safety Monitoring Committee: The Safety Monitoring Committee reviews AEs in a blinded fashion. The committee considers whether changes in the protocol (monitoring, consent process, etc.) are indicated based on the occurrence, frequency, or severity of AEs. The committee also evaluates whether there is any clustering of AEs by clinic. Any concerns on the part of the Safety Monitoring Committee may be referred to the Safety Review Officer and/or DSMB, which can review SAEs in an unblinded manner.
- Safety Review Officer: The Safety Review Officer will review all SAEs in an unblinded fashion and will confirm or reject the causality determination of the SAE to study intervention. As deemed necessary, he/she may contact the local site PI to obtain additional information about the SAE. Any concerns on the part of the Safety Review Officer may be referred to the DSMB.

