# **9 STATISTICAL CONSIDERATIONS**

All analyses will be conducted under the intention-to-treat principle using the treatment as assigned to each subject, and using all available data from all subjects. We will assess the distributional characteristics of all variables and will adjust the analysis accordingly by employing transformations or robust (model free) or nonparametric (distribution free) methods.

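### Section 4.6 makes no exception to its no-masking rule for image post-processing or for data-dependent analysis choices, neither of which needs the arm

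*Combined protocol and SAP*

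**What the plan says.** Section 4.6 reads: "No masking will be employed. The study team and each individual participant will be aware of his/her treatment allocation". Section 8.5 repeats that treatments are not masked.

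Sections 7.2.2 and 8.4 contain the one exception. In the first, "The RISE SMC will review AEs in a blinded manner"; in the second, "SAEs will be monitored by the RISE Safety Monitoring Committee, which will remain blinded to treatment arm". Section 7.2.3 adds, of everything outside the recruitment database: "Only study IDs will be used in all other study databases".

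On imaging, section 6.2.5 says "Approximately 80 5mm axial slices are obtained from the top of the liver to the pelvis" and "SliceOmatic (Tomovision, Inc.) is used for post-image processing to compute subcutaneous and visceral adipose tissue volume and fractional fat content of liver and pancreas". Section 6.2.4 has DEXA body fat computed by the manufacturer's software, with results passed on so that fat can be analysed by region of interest. Neither section names a reader or says whether the reader sees the arm.

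On analysis, section 9 says that the team will look at the distributions of all variables and "will adjust the analysis accordingly by employing transformations or robust (model free) or nonparametric (distribution free) methods". Section 2.4.1 says that the relation between beta-cell measures and insulin sensitivity will be examined first. A disposition index or some better-suited alternative will then be used, in primary as well as secondary analyses. Section 11.1 gives the BetaFat Data Center both the coordination of the study and the analysis of its primary results. Nothing withholds the arm from it.

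**The concern.** Section 1.2 states a directional hypothesis, that banding will do better than metformin. In an open-label trial with such a hypothesis, steps that allow judgement are best done without the arm wherever that is possible.

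Two groups of steps qualify. Depot volumes and organ fat are derived from about 80 slices per scan, and section 6.2.5 does not say that the processing is fully automatic. These measures are secondary (section 3.3.7), but Aim 3 rests on them. The second group matters more. The form of the insulin-sensitivity adjustment and the transformation both help to define the co-primary endpoints of section 3.2, and both are left to be settled from the data. If they are settled by people who can see results by arm, a reader of the trial cannot exclude that the result influenced the choice.

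**Working it through.** The plan gives no figure on masking, so the check is mainly a comparison of sections.

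**1. The plan's own figures, to confirm that the change leaves them alone (section 9.3).**
- Retention: 44 × 0.9² = 35.6 per arm (stated ~35).
- Two-sided t-test, alpha 0.05, 35 per arm, effect 0.68 SD: power 80.1% (stated 80%).
- ANCOVA with r = 0.5: residual SD = √(1 − 0.5²) = 0.866. Power is 89.9% for 0.68 (stated 89%) and 80.2% for 0.59 (stated 80%).

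These reproduce to within a point. None depends on masking.

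**2. Which steps need the arm?**
- *Band adjustment, metformin titration, participant contact:* yes. They cannot be masked.
- *Clamp infusion (section 6.2.3):* staff adjust it during the test from 5-minute glucose values. The infusion rate enters the insulin-sensitivity term of both co-primary endpoints. The participant is present, so coded files do not help.
- *C-peptide and insulin assays:* shared assays run in a central laboratory (section 11.1), with little room for judgement.
- *MRI and DEXA post-processing:* no need for the arm. No masking is stated.
- *Transformation and insulin-sensitivity adjustment:* no need for the arm. No masking is stated. Baseline clamps are complete before randomization (section 4.5), so part of this work can use data that carry no arm at all.
- *Switch to rate of change (section 9.5):* triggered by a between-arm difference in follow-up time. It does need the arm and lies outside this point.

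**3. What an arm-related reading error would do to Aim 3.** Let Z = 1 for band and 0 for metformin, F the true fat measure, R = F + bZ the reading with a constant shift b in the band arm, and Y a beta-cell outcome.
- Within an arm: cov(R, Y) = cov(F, Y) and var(R) = var(F). The slope does not change.
- Across arms at 1:1: cov(R, Y) = cov(F, Y) + bΔY/4 and var(R) = var(F) + bΔF/2 + b²/4, where ΔY and ΔF are the differences between arms. The pooled slope changes.
- Comparison of arms on fat: ΔR = ΔF + b.

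Section 9.2 plans analyses both within and across arms. A constant shift threatens only the across-arm analyses and the direct comparison of arms on fat.

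**4. Is coded working feasible?** The safety committee already works blinded in this open-label trial, and study IDs already replace names outside the recruitment database. An ID does not by itself hide the arm or the visit order, so a further code is needed.

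**The case against.** The best defence is that section 4.6 merely describes open-label treatment, as section 8.5 suggests, and that the outcomes are largely protected. Steady state is a fixed window of 100–120 minutes, the shared assays are central, section 9 uses all available data, and section 9.1 already fixes ANCOVA with a robust covariance. Images are processed with software and study IDs are in use. The follow-up scans that carry the outcome cover the region of the band, so coding them may not mask them. The choice of transformation is, on this view, a matter of pre-specification rather than masking.

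Much of this stands, and it rules out four stronger readings that a reader might infer:
- *Section 4.6 excludes all masking.* It does not, because sections 7.2.2 and 8.4 keep the safety committee blinded.
- *Image readers are known to see the arm.* This is only an inference from the reference to the study team; no reader is named.
- *Someone judges clamps valid or invalid with the arm in view.* No such step is described.
- *The false-positive rate rises to about 8–16%.* With SE = √(2/35) × √0.75 = 0.207 SD, a shift of 0.1 or 0.2 SD would give 7.6% or 15.9%. But that shift is an assumption with no support in the documents, and r = 0.5 is stated for the beta-cell outcome, not for imaging. A null of no difference in fat is also of little interest when section 9.3 cites a 35 lb average loss with banding.

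What the defence does not answer is that the plan leaves the insulin-sensitivity adjustment and the transformations open, with no statement that they are chosen without the arm. Fixing ANCOVA does not fix the variable that enters it.

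**Conclusion.** The point holds as a low-cost improvement. The no-masking rule is stated without an exception for image post-processing or for data-dependent analysis choices, and neither needs the arm. The imaging part concerns secondary endpoints and the across-arm side of Aim 3. The analysis-choice part reaches the co-primary endpoints and is the more important of the two.

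The size of any bias cannot be derived from the documents, and none is claimed here. C-peptide values are little exposed, and the live clamp infusion stays unmasked whatever is done. The conclusion assumes that post-processing leaves some room for judgement, which the plan neither says nor rules out.

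**What to change.** Reword section 4.6 along these lines:
- Participants and treating staff are not masked. The RISE Safety Monitoring Committee remains blinded, as sections 7.2.2 and 8.4 already say.
- MRI and DEXA are analysed by the same readers from files coded for participant, arm and visit order.
- Transformations, the method of insulin-sensitivity adjustment and any exclusion of clamp data are fixed and dated on data with the arm withheld or scrambled, before the arm is joined.

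Sections 2.4.1 and 9 should refer to the last item.

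The cost is a little relabelling and some data-center work to hold back the arm variable. Staff, procedures and sample size stay the same. The downside is that follow-up scans are only partly masked where the band or port can be seen; the plan should say so.
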